### **3.7 Statistical Analyses**

Summary tabulations will be presented that will display descriptive statistics for each treatment group. For subject disposition, demographic and baseline characteristics, medical history, gastrointestinal disease history, and prior medications, an overall column (i.e., all subjects combined) will be included. For continuous variables, descriptive statistics will include the number of subjects, mean, standard deviation, minimum, median, and maximum values. For categorical variables, descriptive statistics will include the number and percent of subjects in each category.

### **3.7.1 Efficacy Analyses**

The primary objective of this study will be to demonstrate the superiority of tenapanor over placebo in the proportion of subjects who are weekly overall responders at 6 or more of the first 12 weeks of treatment.

The ITT analysis set will be used for the analysis of the primary, key secondary, secondary, and all sensitivity analyses. The PP analysis set will be used for the analysis of the primary, key secondary, and secondary variables as a separate sensitivity analysis. All efficacy analyses will be carried out based on observed cases (OC) with imputation as described previously in [Section 3.3](#).

All efficacy variables involving responder rates or proportions will be analyzed using a Cochran-Mantel-Haenszel (CMH) test with pooled investigator site as a stratification (adjustment) variable. These analyses include subject based variables and variables summarized weekly. Summary statistics will include the pairwise risk difference with placebo along with the asymptotic 95% confidence interval (CI). The adjusted relative risk (adjusted for pooled investigator site) will be based on the ratio of responder rates for tenapanor 50 mg BID versus placebo. The 95% CI versus placebo will also be presented for the adjusted relative risk.

All change from baseline or percent change from baseline continuous efficacy variables derived from the daily IVRS questions (i.e., average weekly CSBMs, SBMs, stool consistency, straining score, abdominal symptoms of pain, discomfort, bloating, fullness, and cramping), as well as the weekly IBS severity, constipation severity, and IBS QOL will be analyzed using an analysis of covariance (ANCOVA) model with terms for pooled investigator site, treatment, and baseline as the covariate. These analyses include variables summarized weekly or on a visit basis.

Actual values for degree of relief of IBS symptoms and treatment satisfaction will be analyzed using an analysis of variance (ANOVA) model with terms for pooled investigator site and treatment.

When the ANCOVA model is implemented, the least square means (LSmeans) will be presented for the actual values and change/percent change from baseline values for each treatment group with the 95% CI. Statistical testing will only be carried out using the change/percent change from baseline since the p-values are the same between the two analyses. Treatment effects will be evaluated based on a 2-sided significance level of 0.050 for the difference in LSmeans between treatment groups. The 95% CI for difference in LSmeans will also be presented. When the ANOVA model is implemented, all of the above statistics will be presented for the actual values.

The Mantel-Fleiss criterion for the CMH test will not be computed. Because the sample size of the two treatment groups is relatively large, the CMH test will be valid. Other secondary analyses using the ANCOVA model or ANOVA model will also not have assumptions testing (e.g., normality, parallelism, or homogeneity of variances) carried out.

A sequential testing procedure will be utilized to control the experiment wise Type I error rate for the primary efficacy variable. Because of the desire to also pre-specify key secondary efficacy variables, the sequential testing procedure will not inflate the overall 5% level. The primary efficacy variable will be tested at the 5% level of significance. If this test is significant, the first key secondary efficacy variable listed in [Table 2-1](#) will be tested at the 5% level. If this test is significant, then the next key secondary efficacy variable is tested at the 5% level. This procedure continues until one of the key secondary variables in the list (8 total variables) results in a p-value >5%. Key secondary efficacy variables up to this point in the list will be declared statistically significant.

In addition to the summaries of the efficacy variables described, figures will be provided depicting the actual means or the change/percent change from baseline for each treatment group at each assessment time. Figures depicting the means for each treatment group over time will be presented for average weekly CSBMs, SBMs, stool consistency, straining score, abdominal pain, discomfort, bloating, cramping, and fullness scores. Figures depicting the means for each treatment group over time will be presented for weekly IBS severity score, constipation severity score, adequate relief of IBS symptoms, and degree of relief of IBS symptoms.

A secondary analysis will also include graphs depicting the cumulative distribution of the percentage reduction from baseline in abdominal pain.

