5.4. Entry Criteria at End of 2-Week Screening Period

In order to be eligible for randomization, subjects must satisfy inclusion/exclusion criteria as described in [Sections 5.2](#) and [5.3](#) and meet the subject reported outcome criteria collected during the 2-week screening period as described below.

Subject eligibility, according to the IBS symptom information captured in the diary during the 2-week screening period, will be determined electronically by the interactive voice-response system and provided to the clinical staff via IWRS..

- Subjects must have ≥ 78 % compliance (≥ 11 of 14 days) with completing the daily assessments via the touch-tone telephone diary
- Subjects must have a weekly stool frequency of < 3 CSBMs (complete spontaneous bowel movements) and ≤ 5 SBMs (spontaneous bowel movements)
- Subjects must have a mean stool consistency score of ≤ 3 using the 7-point Bristol Stool Form Scale (BSFS) (see [Appendix B](#))
- For the daily assessment of abdominal pain, subjects must have an average weekly abdominal pain score of ≥ 3 on a 0-10 point scale.
- Rescue medication as defined in [Section 5.5](#), usage for ≤ 2 of the 14 days; none within 48 hours prior to randomization
- No use of a prohibited medication, except rescue medication as defined in [Section 5.5](#)
- No watery stools (Type 7 on the Bristol Stool Form Scale; (see [Appendix B](#)) for any SBM, or loose (mushy) stools (Type 6 on the BSFS) for > 1 SBM

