## **2.3 Efficacy and Safety Variables**

### **2.3.1 Efficacy Variables**

Efficacy variables in this trial will be captured via the IVRS on a daily basis (CSBM frequency, SBM frequency, consistency, straining, and abdominal symptoms of pain, discomfort, bloating, fullness, and cramping) or weekly basis (IBS severity, and constipation severity) during the screening (baseline) period and the 26 week treatment period. Adequate relief of IBS symptoms and degree of relief of IBS symptoms will be collected weekly during the treatment period. The IBS-QOL will be collected at the randomization visit, the week 12 visit, and the week 26 visit. Treatment satisfaction will be recorded at the end of each month during the treatment period through week 20 and again at week 26 Use of rescue medication is also collected daily throughout the screening and treatment periods. Rescue medication usage is incorporated into the derivation of the efficacy variables but is not in itself considered an efficacy variable.

The primary efficacy variable will be the overall responder rate. An overall responder will be defined as a weekly responder for the first 6/12 weeks where both CSBM and abdominal pain response criteria were met for the week. The CSBM and abdominal pain response criteria are defined below. The weekly overall responder rates will be summarized for each week of the treatment period. An endpoint week will be defined as the last valid week during the treatment period with an overall responder criteria assessment.

The CSBM response criteria are defined as an increase of one or more change in average weekly CSBMs from baseline. The definition of a CSBM is as follows: A CSBM is a SBM for which the subject responds “yes” to the following question; “Did you feel like you completely emptied your bowels?” Any SBM which is preceded within 24 hours by the use of rescue medication will not be counted as a SBM and therefore also not counted as a CSBM as defined above. Should a subject not have data reported for a given week (either due to a gap in reporting or due to discontinuation), the subject will be considered to be a non-responder for the week.

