A key secondary efficacy variable will be the overall CSBM responder rate. An overall CSBM responder will be defined as a weekly CSBM responder for the first 6/12 weeks where the CSBM response criteria were met for the week. The weekly CSBM responder rates will be summarized for each week of the treatment period. An endpoint week will be defined as the last valid week during the treatment period with a CSBM response criteria assessment.

The average weekly CSBMs will be calculated as the sum of the number of CSBMs reported during each day of the defined weekly period divided by the number of days CSBMs were reported multiplied by 7. A valid week will require at least 4 days of SBM reporting. The average weekly CSBMs and change from baseline (where baseline is the average of the 2-weeks during the screening period) for each week of the treatment period will be summarized. An endpoint week will be defined as the last valid week during the treatment period with an average weekly CSBM.

The abdominal pain response criterion is defined as a decrease of 30% or more of percent change in average weekly worst abdominal pain from baseline. Abdominal pain will be scored daily using the scale 0 = No pain to 10 = very severe pain. The average weekly abdominal pain score will be calculated as the average score for all days during a valid week. A valid week will require at least 4 days of abdominal pain reporting. Should a subject not have data reported for a given week (either due to a gap in reporting or due to discontinuation), the subject will be considered to be a non-responder for the week.

The average weekly abdominal pain score and percent change from baseline (where baseline is the average of the 2-weeks during the screening period) for each week of the treatment period will be summarized. An endpoint week will be defined as the last valid week during the treatment period with an average weekly abdominal pain score.

A key secondary efficacy variable will be the overall abdominal pain responder rate. An overall abdominal pain responder will be defined as a weekly abdominal pain responder for the first 6/12 weeks where the abdominal pain response criteria were met for the week.

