### **3.5 Visit Windows**

Daily IVRS diary data are planned for daily collection starting on the day of the Screening visit and continuing until the planned Week 26 (Visit 9 Day 183).

Weekly IVRS diary data are planned for each week of the 2-week screening period (when applicable), and each week of the 26-week treatment period.

For all IVRS efficacy data, the date collected will be used to calculate a relative study day (Rel Day). The relative study day will be calculated as the number of days from the day of first dose. The day of the first dose date is Day 1. The preceding day is Day -1, the day before that is Day -2, etc. There is no Day 0.

Actual study periods will be defined as follows for the purposes of the efficacy evaluations:

- Screening/Baseline Period (Rel Days -14 through Day -1): For the average weekly CSBMs, average weekly SBMs, average weekly stool consistency, average weekly straining score, and average weekly abdominal symptom score (pain, discomfort, bloating, cramping, and fullness), the most recent 7 days will be used to calculate Week -1 values (i.e., days -1 through -7) and remaining days will be used for Week -2 calculations (i.e., day -8 through -14 or more if applicable). The baseline for these variables will then be based on the average of the week -2 and week -1 values. While the screening period may vary somewhat from 14 days, it will generally be required that subjects provide two weekly ratings of the weekly IVRS diary questions during this period.
- Treatment Period:
  - Week 1 (Rel Day 1-7)
  - Week 2 (Rel Day 8-14),
  - Week 3 (Rel Day 15-21),
  - Week 4 (Rel Day 22-28),
  - Week 5 (Rel Day 29-35),
  - Week 6 (Rel Day 36-42),
  - Week 7 (Rel Day 43-49),
  - Week 8 (Rel Day 50-56),
  - Week 9 (Rel Day 57-63),
  - Week 10 (Rel Day 64-70),
  - Week 11 (Rel Day 70-77),
  - Week 12 (Rel Day 78-84), and
  - Week 13 through Week 26 (Rel Day 85-183 divided by 7 day weeks).

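### The responder analyses, including the primary, leave baseline CSBM frequency and baseline pain out of the model; adding them is a cheap efficiency and robustness gain, not the repair of an error

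*SAP*

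**What the plan says.** Under SAP 3.7.1 all responder variables are "analyzed using a Cochran-Mantel-Haenszel (CMH) test with pooled investigator site as a stratification (adjustment) variable". Protocol 10.7.6 specifies the same test. No baseline term appears.

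The next paragraph of SAP 3.7.1 handles change from baseline in the continuous outcomes, including average weekly CSBMs and abdominal pain, by an ANCOVA "model with terms for pooled investigator site, treatment, and baseline as the covariate".

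Both baselines exist for every subject who passes screening. SAP 3.5 derives them from the two diary weeks: "The baseline for these variables will then be based on the average of the week -2 and week -1 values". SAP 2.3.1 then defines weekly response against them, as "an increase of one or more change in average weekly CSBMs from baseline" for CSBMs and "a decrease of 30% or more of percent change in average weekly worst abdominal pain from baseline" for pain. For the 9/12 CSBM criterion it adds a floor of at least 3 CSBMs in the week.

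The sensitivity analyses in SAP 2.3.1, Table 2-1 and sections 3.2 to 3.4 vary the imputation of missing weeks, the pain threshold, the pooling of sites or the analysis set. None adds baseline to a responder analysis.

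**The concern.** Measuring an outcome relative to baseline is not the same as adjusting the comparison for baseline. The plan accepts this for continuous outcomes, where change from baseline still gets a baseline covariate. For responder outcomes it stops at pooled site.

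Randomisation is stratified by site only. Nothing in the design balances baseline severity, and nothing in the responder model corrects a chance imbalance. If the baselines predict response, the plan forgoes some precision on the primary and key secondary comparisons and has no pre-specified check on whether an imbalance contributed to the result. The eight key secondaries are tested in fixed order and the first miss ends the sequence, so a small loss of power at one step can cost the claims behind it.

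**Working it through.** **1. The plan's own figures.** Inputs from SAP 3.1: 300 per arm, two-sided Fisher's exact test at 0.05, a 15-point difference with tenapanor at 45% (so 45% vs 30%), and an 11.6-point difference (taken as 45% vs 33.4%). Exact enumeration gives 96.1% against the stated 95%, and 80.8% against the stated 80%. With rates centred on 50%, the least favourable case, it gives 95.4% and 80.2%. The stated power reproduces.

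**2. Effect of adjustment.** Let R² be the share of responder-status variance explained by the two baselines. Then

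- SE = √{[p₁(1−p₁) + p₂(1−p₂)]/300}
- the CI width is multiplied by √(1−R²)
- power = Φ(Δ/(SE·√(1−R²)) − 1.96)

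For 45% vs 30%, SE = √(0.4575/300) = 0.03905 and Δ/SE = 3.841. For 45% vs 33.4%, SE = √(0.46994/300) = 0.03958 and Δ/SE = 2.931.

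| Assumed R² | CI width × | Power, 15 points | Power, 11.6 points |
|---|---|---|---|
| 0 | 1.000 | 97.0% | 83.4% |
| 0.01 | 0.995 | 97.1% (+0.1) | 83.8% (+0.4) |
| 0.03 | 0.985 | 97.4% (+0.4) | 84.5% (+1.1) |
| 0.05 | 0.975 | 97.6% (+0.6) | 85.3% (+1.8) |
| 0.10 | 0.949 | 98.2% (+1.2) | 87.1% (+3.6) |

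These are normal approximations and sit slightly above the Fisher values, so the gains matter more than the levels. A pooled-variance version starts at 96.8% and 83.1% and gives the same gains to within 0.1 point. In effective sample size, R² of 0.05 to 0.10 corresponds to 300/0.95 = 316 to 300/0.90 = 333 per arm.

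**3. Check against the CMH itself.** In 3,000 simulated trials per scenario, with ten pools, the pool-stratified CMH was compared with a baseline-adjusted risk difference (linear model, robust SE).

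- R² about 0.05: 96.0% vs 97.1% at 15 points, and 82.0% vs 84.3% at 11.6.
- R² about 0.10: 97.0% vs 98.0%, and 82.0% vs 86.4%.
- R² zero: 96.7% vs 96.5%, and 82.9% vs 83.1%, so no gain and no cost.

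**4. How large R² might be.** The documents give no figure. An illustrative diary simulation of the 6/12 overall endpoint, with the entry limits applied and improvement assumed unrelated to baseline, gave R² of 0.005 to 0.032. That narrows the interval by 1−√0.995 = 0.3% to 1−√0.968 = 1.6%. It captures only the dependence built into the endpoint. The 0.05 to 0.10 rows need genuine prognostic strength on top of that.

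**5. The 9/12 CSBM criterion.** For 6/12 and 13/26 the required gain is 1 CSBM per week at any baseline. With the floor, the required gain is max(1, 3 − baseline): 3 from a baseline of 0, 2 from 1, and 1 from 2 or above. Baseline here sets the size of the improvement required. In SAP Table 2-1 the three 9/12 variables stand third to fifth among the key secondaries, ahead of all three 13/26 variables. The documents give no 9/12 response rates, so no power is computed for them.

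**The case against.** The case for leaving the plan alone is substantial.

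- The CMH is valid. Randomisation is blocked within site, the test stratifies on pools of sites, and its Type I error already allows for chance baseline imbalance. This stands.
- Baseline is built into the endpoint, and entry narrows its range: "Subjects must have a weekly stool frequency of < 3 CSBMs", with mean pain of at least 3. Dichotomising a change also means that the gain from ANCOVA does not carry over one for one. This stands, and it is why the low R² rows are the better-supported ones.
- A reader might infer dependence from the raw hurdles alone: a 30% fall is 0.9 points from a baseline of 3 but 2.4 points from 8. That shows the threshold moving, not the probability of response. For the 6/12 endpoint the inference is not supported. The 9/12 floor is different, because there the required CSBM gain itself changes.
- Protocol section 10 says the primary and key secondary analyses will stay as they are, and SAP section 1 rules out deviating from the primary analyses. This weighs against replacing the CMH. It does not bar an added analysis: the same protocol section lets the SAP pre-specify further sensitivity analyses and address changes to the statistical section.
- Baseline values are tabulated by arm (SAP 3.6.2), so an imbalance would be visible. But a table does not show what the imbalance did to the responder difference.

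**Conclusion.** The omission is real: baseline CSBMs and pain are absent from every responder model and from every listed sensitivity analysis, although the plan adjusts for them elsewhere. Correcting it improves efficiency and robustness.

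The size rests wholly on an assumed R². At 0.01 to 0.03 the gain is slight, at most about 0.4 points of power at the design difference and 1.1 points at 11.6. At 0.05 to 0.10 it is useful for smaller effects, about 2 to 4 points at 11.6. At zero there is none. The benefit is probably greatest for the 9/12 CSBM rate, and for the 9/12 overall rate insofar as it uses the same CSBM criterion. That is a judgement from the definition, not a computed result.

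Two stronger readings are tempting and the documents support neither. One is that the primary test is biased or the trial underpowered: the test is valid and both stated powers reproduce. The other is that a loss of precision is established: it depends on prognostic strength that is nowhere reported.

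**What to change.** Before unblinding, add to SAP 3.7.1 a baseline-adjusted analysis of the primary and key secondary responder rates. Use logistic regression with treatment, pooled site, baseline average weekly CSBMs and baseline average weekly worst pain. Report the standardised risk difference with a robust 95% CI, which keeps the same risk-difference target.

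If the protocol section 10 and SAP section 1 commitments are read as fixing the primary test, keep the CMH as the confirmatory test throughout the sequence and report the adjusted analysis beside it. State which of the two is confirmatory.

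The cost is a short SAP paragraph and a little programming, with no new data. The downside is small: the added analysis depends on a model.

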Average weekly SBMs will be calculated as described above for average weekly CSBMs. Change from baseline for each week of the 26-week treatment period will be summarized using the observed data. An endpoint week will be defined as the last valid week during the treatment period with an average weekly SBM.

Subjects will record the consistency of each of their bowel movements on a daily basis through the IVRS utilizing the BSFS scale (Appendix B of the protocol). The average weekly stool consistency will be calculated as the average score for all valid SBMs during the week. For purposes of calculating an average, days with no stools will be scored a 0. Change from baseline for each week of the 26-week treatment period will be summarized using the observed data. Baseline will be calculated as described for the CSBMs and SBMs. An endpoint week will be defined as the last valid week during the treatment period with an average weekly stool consistency.

Straining will be scored for each SBM using the scale 1 = not at all, 2 = a little bit, 3 = a moderate amount, 4 = a great deal, 5 = an extreme amount. The average weekly straining score will be calculated as the average score for all valid SBMs during the week. Change from baseline for each week of the 26-week treatment period will be summarized using the observed data. Baseline will be calculated as described for the CSBMs and SBMs. An endpoint week will be defined as the last valid week during the treatment period with an average weekly straining score.

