Abdominal discomfort, abdominal bloating, abdominal fullness, and abdominal cramping will be scored daily using the 0-10 point scale with 0 representing no presence of the symptom and 10 representing very severe presence of the symptom. The average weekly scores will be calculated as the average score for all days during a valid week. Percent change from baseline for each week of the 26-week treatment period will be summarized. In addition, responders at each week (i.e., 30% improvement from baseline) and for the first 6/12 weeks, 9/12 weeks, and 13/26 weeks on treatment will be defined in a similar manner as for abdominal pain responder rates. If no data is present to constitute a valid week, it will be assumed the subject did not respond. Otherwise, observed data will be used to summarize the average weekly abdominal symptom. Baseline will be calculated as described for the CSBMs and SBMs. An endpoint week will be defined as the last valid week during the treatment period with an average weekly abdominal symptom score. Each symptom will be assessed separately so it is possible for different symptoms to have different endpoint weeks.

IBS severity and constipation severity will be scored on a weekly basis using the scale 1 = None, 2 = Mild, 3 = Moderate, 4 = Severe, 5 = Very Severe. IBS severity scores and constipation severity scores for each week of the study will be summarized as categorical and continuous data. Observed data will be used for the summaries. Baseline for these severity ratings will be the average of the two ratings during the screening period. An endpoint week will be defined as the last valid week during the treatment period with an IBS severity or constipation severity rating.

Adequate relief of IBS symptoms (1 = yes, and 2 = no) will be asked on a weekly basis during the treatment period. The percentage of subjects with adequate relief for each week of the study will be summarized using observed data. An endpoint week will be defined as the

last valid week during the treatment period with an adequate relief of IBS symptoms response.

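### The SAP says tests on actual values and on change or percent change give the same p-value; this is false for percent change, the measure named for the five abdominal symptom scores (minor)

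*SAP*

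**What the plan says.** SAP 3.7.1 applies an ANCOVA with treatment, pooled investigator site and baseline to "All change from baseline or percent change from baseline continuous efficacy variables derived from the daily IVRS questions", and also to the weekly severity ratings and the IBS-QOL. It does not say there which variables use change and which use percent change.

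For presentation, "the least square means (LSmeans) will be presented for the actual values and change/percent change from baseline values for each treatment group". For testing: "Statistical testing will only be carried out using the change/percent change from baseline since the p-values are the same between the two analyses". Protocol 10.7.6 gives the same reason in the same words. SAP 3.7.1 evaluates treatment effects at a two-sided 0.050 level and adds: "The 95% CI for difference in LSmeans will also be presented". The scale of that interval is not named.

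SAP 2.3.1 indicates the scale by variable:

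- Abdominal pain: "The average weekly abdominal pain score and percent change from baseline" are summarised weekly.
- Discomfort, bloating, fullness and cramping: "Percent change from baseline for each week of the 26-week treatment period will be summarized".
- SBMs, stool consistency and straining: "Change from baseline for each week of the 26-week treatment period will be summarized using the observed data". CSBMs also use absolute change.

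So percent change is the only change measure named for the five abdominal symptom scores. SAP 3.6 makes all secondary p-values descriptive.

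**The concern.** The sentence in SAP 3.7.1 treats change and percent change as one case. The equality it relies on is a standard property of ANCOVA on absolute change, and it does not carry over to a ratio.

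The report would show actual-value LS means for each arm and one p-value, with the plan asserting that this p-value serves both scales. For the five symptom scores it serves only percent change. A reader could call an actual-value difference significant, or not significant, on a test that was never done on that scale.

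A smaller matter follows from the same choice. Percent change is undefined at a zero baseline. Protocol 5.4 requires an average pain score of at least 3 at entry, but sets no minimum for the other four symptoms, which are scored 0–10.

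**Working it through.** **1. The plan's statement, checked by algebra.** Let Y be the on-treatment weekly score, B the baseline and T the treatment indicator.

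- Actual value: Y = α + τT + βB + site + ε.
- Absolute change: Y − B = α + τT + (β − 1)B + site + ε. Only the baseline coefficient moves, by 1. Residuals, τ, its standard error and its p-value are identical, so here the plan is right.
- Percent change: 100(Y − B)/B = 100·Y/B − 100. The constant goes into the intercept, but each Y has been divided by that subject's own B. This is not a linear shift, so the estimate, standard error and p-value all change.

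Example: two subjects with baselines 4 and 8 each fall by 2 points. Their absolute changes are equal. Their percent changes are 100 × (−2)/4 = −50 and 100 × (−2)/8 = −25.

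**2. Why the direction is not fixed.** If residual SD is a constant 2.0 points, the SD of percent change is 100 × 2.0/B: about 67 at B = 3, 34 at B = 5.9 and 22 at B = 9. Low-baseline subjects then add disproportionate noise. If instead residual SD is 2.0 × B/5.9, the SD of percent change is 100 × 2.0/5.9 = 34 at every baseline, and percent change becomes the steadier scale.

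**3. Size, by simulation.** Taken from the documents: 300 per arm (SAP 3.1), 10 site pools of 60 (SAP 3.4), the ANCOVA terms and two-sided 0.05 (SAP 3.7.1), and the pain minimum of 3 (Protocol 5.4). The documents give no means or SDs for these scores, so everything else is assumed:

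- baseline normal with mean 5.9 and SD 1.7, limited to 0–10 (3–10 for pain);
- outcome mean 0.7 × baseline, outcome limited to 0–10;
- effect −0.6 (additive) or −0.6 × B/5.9 (proportional);
- residual SD constant or scaled as in step 2; site SD 0.2.

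There were 3,000 trials per setting. Zero baselines were dropped from the percent-change model only. Actual-value and absolute-change p-values agreed to within 5 × 10⁻¹³.

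| Score | Residual SD | Effect | Power, absolute | Power, percent | Conclusions differ at 0.05 |
|---|---|---|---|---|---|
| Non-pain | constant | additive | 0.95 | 0.92 | 5% |
| Non-pain | constant | proportional | 0.96 | 0.85 | 11% |
| Non-pain | scaled | additive | 0.94 | 0.98 | 4% |
| Non-pain | scaled | proportional | 0.94 | 0.95 | 3% |
| Pain | constant | additive | 0.96 | 0.94 | 3% |
| Pain | constant | proportional | 0.96 | 0.91 | 5% |
| Pain | scaled | additive | 0.95 | 0.98 | 4% |
| Pain | scaled | proportional | 0.94 | 0.95 | 3% |

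**4. Sensitivity to lower or wider baselines (non-pain scores, constant SD; additive then proportional effect).** With baseline mean 5.0, power for absolute vs percent change is 0.95 vs 0.85 and 0.87 vs 0.61. With baseline SD 2.0 it is 0.96 vs 0.86 and 0.95 vs 0.73. Conclusions differ in 11–27% of these trials. With scaled SD at the same baselines they differ in 2–5%.

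**5. Type I error.** Over eight null settings the percent-change test rejected in 4.6–5.6% of trials. The simulation standard error is √(0.05 × 0.95/3,000) = 0.4 percentage points, so this is consistent with 5%.

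**6. A single simulated trial** from a separate model (pain-like baseline of at least 3, mean 6.3, SD 1.6): p = 0.0033 for actual value, 0.0033 for absolute change and 0.00045 for percent change.

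**7. Zero baselines.** The expected number is about 0.2 per 600 subjects in the main model, and about 1 with the lower or wider baselines of step 4.

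**The case against.** The strongest reply is that nothing confirmatory depends on this. The five scores are secondary, their p-values are descriptive, and the primary and eight key secondary variables are responder rates tested by CMH. Percent change is prespecified in SAP 2.3.1, matches the 30% responder rule and holds its Type I error. Actual-value LS means with confidence intervals are already planned. All of that stands, and it is why the point is minor.

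It does not rescue the sentence. The stated reason for leaving actual values untested is untrue for these scores, and displaying the actual-value means beside a percent-change p-value invites the misreading.

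A reader might infer that percent change is the wrong scale and should give way to absolute change. The documents do not support that. With residual SD scaling with baseline, percent change had equal or higher power in every setting examined, and the plan gives no data to say which variance structure applies. SAP 3.7.1 also states that "Other secondary analyses using the ANCOVA model or ANOVA model will also not have assumptions testing" carried out, so the plan itself will not show which case holds; such testing would not settle the choice of scale in any event.

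A reader might also infer that zero baselines seriously damage the analysis. A zero baseline needs a score of 0 on every recorded day in both screening weeks, in subjects with active IBS-C and diary entries on at least 11 of 14 days. That should be rare. SAP section 4 also places the programming specifications in a separate document that was not available for this review, so a rule may exist there.

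**Conclusion.** The statement of equal p-values is exact for absolute change and false for percent change. That conclusion is algebraic and needs no assumption about the data. It reaches all five abdominal symptom scores, because percent change is the only change measure SAP 2.3.1 names for them.

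The size does rest on assumptions. Conclusions at 0.05 differ in roughly 3–11% of trials under the main inputs, and in up to 27% if baselines are lower or more spread and residual SD is constant. The direction can go either way.

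A reader might take this as a threat to the trial's error control or its main results. It is not: Type I error is not inflated, and the primary and key secondary CMH tests do not use these models. Severity is minor. The plan claims a property for a set of descriptive tests that those tests do not have.

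**What to change.** In SAP 3.7.1:

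- Limit the statement about equal p-values to absolute change from baseline.
- For abdominal pain, discomfort, bloating, fullness and cramping, keep the percent-change ANCOVA. Also report the treatment test, LS mean difference and 95% CI from the ANCOVA on the actual value (equivalently absolute change), with treatment, pooled investigator site and baseline.
- Label every p-value and confidence interval with its scale.

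The actual-value analysis also keeps any subject whose baseline is zero. As a small addition, SAP 2.3.1 could carry one line on how a zero baseline is handled in the percent-change and 30% responder summaries of the four non-pain symptoms, including whether the subject stays in the responder denominator.

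The cost is one paragraph, one optional line, and a second run of an existing model. The downsides are one extra descriptive p-value per score and time point, and occasional disagreement between the two scales that the report must explain. Protocol section 10 allows changes to its statistical section to be made in the SAP without a protocol amendment, and the primary and key secondary analyses stay as they are.
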